Subjects who discontinue study drug before the end of the study treatment period will enter a non-treatment, follow-up phase, in which subjects will follow their visit schedules with modified assessments until study completion. Subjects will attend a post-study visit at Week 104, for assessment of measures of growth and maturity. This visit should be completed without delay at 104 weeks (+7 days) from Day 1, regardless of whether any other study visits were delayed.

All subjects with HbA1c > 8.0% at and after Week 26 will be rescued.

Discontinued subjects will still be evaluated for rescue and will not be replaced.

The Investigator, Sponsor, site and subject will be blinded to the subjects' HbA1c results following administration of IP on Day 1 until after study completion. In the event of an HbA1c result > 8.0% during the LT treatment period (when these values require subject rescue), the investigator will be informed via an HbA1c alert from the central laboratory but will remain blinded to the HbA1c result.

Revised Protocol No: 06

During the course of the trial, subjects may be eligible for the addition of open-label rescue medication to their blinded treatment regimen in order to treat ongoing hyperglycemia. Insulin may be used as rescue, at the Investigator's discretion. Any permanent changes in dose of basal insulin should be done after evaluation of rescue criteria, including both self-monitoring blood glucose (SMBG) and central laboratory FPG values.

Pre-specified glycemic criteria (see Table 1 below), based upon SMBG, FPG, or single central laboratory FPG and repeat confirmatory FPG have been established during the treatment period, starting at Week 6, and up to but not including the Week 52 visit, to determine eligibility for open-label rescue medication.

Table 1: Lack of Glycemic Control Criteria for Initiation of Rescue Medication

| Study week | Rescue criterion |
|---|--|
| Week 6 visit up to and not | FPG>13.3 mmol/L (240 mg/dl) based on 3 consecutive fasting SMBG values followed by a confirmatory central laboratory FPG |
| including Week 26 visit | or |
| | Single central laboratory FPG followed by a confirmatory central laboratory FPG |
| | FPG>10 mmol/L (180 mg/dl) based on SMBG for 3 consecutive days followed by a confirmatory central laboratory FPG |
| Week 26 visit up to and not including Week 52 visit | or |
| | Single central laboratory FPG followed by a confirmatory central laboratory FPG |
| | or |

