8.4.3.1 Short-term and Long-term Assessment

The number and percent of subjects with at least one AE will be summarized for each treatment group, including summaries of AEs, SAEs, and AEs leading to discontinuation. Summaries will include the number of subjects with events by system organ class and preferred term. In addition, the proportion of subjects experiencing at least one episode of hypoglycemia during the 26 weeks of ST treatment and 52 weeks of treatment (ST+LT) will be summarized by treatment group.

The incidence of marked laboratory abnormalities through 26 weeks (ST), and separately, through 52 weeks (ST+LT) will be summarized for each treatment group.

Values and changes from baseline at each scheduled time point for clinical laboratory parameters, body weight and vital signs, including seated BP and HR, will be summarized by treatment group using descriptive statistics. The normality/abnormality of ECG tracings, as determined by the Investigator, will be summarized by shift tables overall and by ECG tracing at baseline. Tanner staging and measures of growth will also be summarized by treatment group using descriptive statistics.

The Treated Subjects Data Set will be used for all safety analyses, including data after rescue (primary safety analysis). Additional sensitivity analyses on data collected prior to rescue will be performed for AEs, hypoglycemia events, and clinical laboratory marked abnormalities. The primary analyses of events of hypoglycemia will be performed excluding data after rescue. Safety analyses will be performed using data from the ST treatment period (at the time of the primary endpoint analysis) and then again at the final database lock (52 weeks) on the combined ST+LT treatment period.

Measures of growth, bone, and maturation markers will be summarized for ST and the combined ST+LT treatment periods.

For these analyses, safety data will be summarized by treatment group based on the treatment received (dapagliflozin/saxagliptin/placebo) using the Treated Subjects Data Set.

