1.2 Study design

The proposed study is a 26-week Phase 3b, multicentre, randomised, placebo-controlled, double-blind, parallel-group study with a 26-week safety extension period to evaluate the safety and efficacy of dapagliflozin (5 mg and 10 mg), and, separately, saxagliptin (2.5 mg and 5 mg) in paediatric subjects with T2DM, and an additional post-study visit at Week 104 for assessment of measures of growth and maturity.

This study will consist of 4 study periods:

- (i) **Screening period.** This period starts with enrolment and ends at the start of the lead-in period.
- (ii) **Lead-in period.** During this 2-week period, subjects will be instructed on a diet and exercise program (in accordance with the American Diabetes Association [ADA] or similar local guidelines) to be followed for the study duration. Subjects will maintain their baseline types and/or doses of antidiabetic therapy throughout the study. No placebo or study medication will be provided during the lead-in period.
- (iii) **26-week double-blind short-term (ST) treatment period.** On the Day 1 visit, subjects who meet all protocol-specific enrolment and randomisation criteria will be randomised.
- (iv) **26-week double-blind long-term (LT) treatment period.** After completing the ST treatment period, all subjects will enter the 26-week LT treatment period.

The 52-week treatment period will be referenced as the ST+LT treatment period.

The **Randomised withdrawal period** is defined, for those subjects eligible for the 3rd randomisation, as the time from 3rd randomisation (Week 32 or Week 40) until end of LT period (Week 52).

Subjects who discontinue IP treatment before the end of the study treatment period will enter a non-treatment, follow-up phase in which subjects will follow their visit schedules with modified assessments until study completion.

In addition, there will be 2 post-study visits:

- (i) **Week 56** (phone visit), to assess AEs and serious adverse events (SAEs).
- (ii) **Week 104** (office visit), to assess measures of growth and maturity, height, weight, AEs and SAEs.

Approximately 243 paediatric subjects aged 10 to below 18 years of age will be randomised in a 1:1:1 ratio to receive dapagliflozin 5 mg, saxagliptin 2.5 mg, or placebo. Approximately 81 subjects will be randomised to each treatment arm.

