1.3 Number of subjects

The sample size for this study was selected to be consistent with the research hypotheses.

Dapagliflozin and saxagliptin will be compared with placebo separately. Within each group of hypotheses, multiplicity adjustment with respect to the comparisons will be made using a hierarchical approach. No comparisons between dapagliflozin and saxagliptin will be performed.

The sample size for this study is based on the ability to detect a 0.75% improvement over placebo for dapagliflozin or saxagliptin in change from baseline in HbA1c at Week 26 (ST) with approximately 80% power for each comparison at a two-sided alpha level of 0.05. If 243 paediatric subjects are randomised and analysed, and each treatment compared to placebo at a 2 sided alpha=0.05 level, this will provide approximately 80% power for each comparison to detect a 0.75% reduction in HbA1c change from baseline versus placebo assuming a standard deviation of 1.7%.

Day 1 Randomisation will be stratified based on the baseline anti-diabetic treatment regimen (stable baseline dose of metformin [IR or XR], a stable baseline dose of insulin, or a stable combination of metformin [IR or XR] and insulin), sex, and age (≥ 10 to < 15 years, ≥ 15 to < 18 years).

The standard deviation estimate of 1.7% is based on a blinded review of the ongoing study data.

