In addition, the overall AE summary will be repeated for subgroups based on race, ethnicity, sex, age group (using randomisation strata), region, baseline antidiabetic treatment, baseline HbA1c and baseline BMI, using the categories defined in the Appendix (Table 19). This will be provided based on the ST+LT period and will include all data regardless of rescue medication initiation and prior to rescue medication initiation. The overall AE summary will also be presented for the subgroup of subjects on a stable baseline dose of metformin IR or XR (with or without insulin).

The number and percentage of subjects with at least one AE will be summarised by SOC, PT and treatment group. AEs will be sorted by decreasing frequency within each SOC and PT according to the overall active treatment group, and, where applicable, by high dose active treatment or active treatment with background medication. As appropriate the number of events will also be displayed.

All adverse events will be summarised by SOC and PT (including incidence rate presented for PTs for the ST+LT period), regardless of rescue medication initiation unless otherwise specified, for:

- The ST period and the combined ST+LT period (including incidence rate).
- The ST period and the combined ST+LT period (including incidence rate), prior to rescue medication initiation.
- The combined ST+LT period, up to Week 32.

- The combined ST+LT period, excluding subjects randomised to withdrawal from metformin. A weighted analysis will be conducted on the Treated Subjects Data Set using the original randomised group and presenting weighted proportions.
- The combined ST+LT period. AEs will be summarised by treatment group received at the time of AE onset. For placebo subjects re-randomised to switch to dapagliflozin (or saxagliptin), AEs will be analysed in the placebo group to the beginning of the randomised withdrawal period and in the dapagliflozin (or saxagliptin) group if the event onset occurs during the randomised withdrawal period. AEs will be presented as incidence rate adjusted for exposure, as described in Section 3.4.1.
- The randomised withdrawal period. AEs with a date of onset occurring after the withdrawal baseline will be summarised using the Randomised Withdrawal Subjects Data Set separately for the three treatment comparisons described in Section 4.1.5.

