4.7.2.4 Hypoglycaemia

Hypoglycaemic events will be included in summaries for the ST, ST+LT and randomised withdrawal periods if their onset falls between the start of IP treatment and the cut-off dates defined for each period in [Table 8](#). The primary analysis will be based on data including

hypoglycaemia events occurring prior to rescue medication initiation; sensitivity analyses will include data after rescue medication initiation.

The number and proportion of subjects with hypoglycaemic events (including those reported as SAEs) will be tabulated in each treatment group by ADA and ISPAD categories (see Section 8.9) for:

- The ST period and the combined ST+LT period, prior to rescue medication initiation (as primary analyses).
- The ST period and the combined ST+LT period, regardless of rescue medication initiation (as sensitivity analyses).
- The combined ST+LT period, up to Week 32, prior to rescue medication initiation (as primary analyses).
- The combined ST+LT period, up to Week 32, regardless of rescue medication initiation (as sensitivity analyses).
- The randomised withdrawal period. The events, with a date onset occurring on or after the randomised withdrawal prior to rescue medication initiation, will be summarised separately for the three treatment comparisons described in Section 4.1.5 using the Randomised Withdrawal Subjects Data Set.

The ST+LT period prior to rescue medication initiation analysis will also be repeated for the subgroup of subjects on a stable baseline dose of metformin IR or XR (with or without insulin).

Hypoglycaemic events that do not fulfil the ADA or ISPAD categories will be presented as ‘Not classified’.

All information (symptoms, risk factors etc.) collected in the separate CRF pages for hypoglycaemic events (whether or not they fulfilled SAE criteria) will be summarised by treatment group and listed for the ST+LT period. For the ST+LT + Week 104 period, the listing will include all data collected up to Week 104.

Hypoglycaemic events meeting SAE criteria will also be presented in the listing.

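### The pre-rescue hypoglycaemia tables by ADA and ISPAD class give crude proportions with no exposure-adjusted rate, so more rescue on placebo can look like more hypoglycaemia on drug over 52 weeks

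*SAP*

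**What the plan says.** SAP 4.7.2.4 states that "The number and proportion of subjects with hypoglycaemic events (including those reported as SAEs) will be tabulated in each treatment group" by ADA and ISPAD category. Its first listed window is "The ST period and the combined ST+LT period, prior to rescue medication initiation (as primary analyses"; an up-to-Week-32 version is also primary before rescue, and each table is repeated regardless of rescue as sensitivity. Protocol 8.4.3.1 agrees: "The primary analyses of events of hypoglycemia will be performed excluding data after rescue". In SAP Table 8, non-serious hypoglycaemia is the only safety row whose primary cut-off includes first rescue intake.

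Rescue depends on glycaemia. Before Week 26 it is triggered by FPG; after that, "All subjects with HbA1c > 8.0% at and after Week 26 will be rescued" (protocol synopsis and 3.1). Under SAP 4.1.1, counting stops at the first recorded rescue insulin, so a subject rescued by diet and exercise alone keeps counting.

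The plan has exposure-adjusted rates elsewhere. SAP 3.4.1 defines one per 100 patient-years, with a pre-rescue version in which the rescue date replaces the last exposure date for subjects without an event. SAP 4.7.1.1 applies it to adverse events by SOC and PT: "The ST period and the combined ST+LT period (including incidence rate), prior to rescue medication initiation". Table 24 lists pre-rescue rates for marked laboratory abnormalities (ST+LT) and for the overall AE summary, which has a line for any hypoglycaemia event; the 4.7.1.1 text makes rates in that summary optional. Protocol 8.4.3.2 includes hypoglycemia among the analyses by treatment received that are to report exposure-adjusted rates. SAP 4.7.2.4 specifies no rate, and SAP Section 6 does not list this as a change.

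**The concern.** Time at risk in the primary hypoglycaemia analysis ends at an event that depends on efficacy. If placebo subjects are rescued more, they have less time in which a pre-rescue event can be counted, and a crude proportion takes no account of that. Two arms with the same hazard would then show different proportions, with drug higher, and the gap would grow with efficacy. Hypoglycaemia is a named safety objective, and the classified tables are where a reader will look for it.

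**Working it through.** **Inputs from the documents.** SAP 1.2: "Approximately 81 subjects will be randomised to each treatment arm". SAP 1.3: the design is to "detect a 0.75% reduction in HbA1c change from baseline versus placebo assuming a standard deviation of 1.7" (per cent), "with approximately 80% power for each comparison at a two-sided alpha level of 0.05". No rescue rate, hypoglycaemia rate or power for hypoglycaemia is stated; all such values below are assumptions.

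**1. The plan's own figure.** SE = 1.7 × √(2/81) = 0.267; 0.75/0.267 = 2.81; Φ(2.81 − 1.96) = 80.2% (noncentral t: 79.7%). The stated 80% is reproduced. It concerns Week 26 HbA1c and fixes only the arm size here.

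**2. Simple 52-week model.** Common first-event hazard h per patient-year; a fraction r rescued just after Week 26 (0.51 years), the rest followed for 1 year:

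proportion = r(1 − e^(−0.51h)) + (1 − r)(1 − e^(−h)).

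With h = 0.3 the two terms are 0.1419 and 0.2592.
- Placebo, r = 0.50: 0.5 × 0.1419 + 0.5 × 0.2592 = 20.1%.
- Drug, r = 0.25: 0.25 × 0.1419 + 0.75 × 0.2592 = 23.0%.

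The ratio is 1.15 with no true difference. Over h = 0.1, 0.3, 0.6 and placebo/drug rescue of 50/25, 60/30, 50/35 and 40/20%, it runs from 1.08 to 1.20.

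**3. Gradual rescue.** Rescue starts at Week 6, and half of the log-survival lost after Week 26 is lost at Week 26. With S(t) the probability of not yet being rescued, proportion = ∫ h·e^(−ht)·S(t) dt. Results at 52 weeks, drug vs placebo:

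| Rescued by Week 52, drug/placebo | h = 0.2 | h = 0.5 | h = 1.0 | Ratio | Years before rescue |
|---|---|---|---|---|---|
| 25% / 40% | 16.1 vs 14.6% | 35.4 vs 32.1% | 57.6 vs 52.9% | 1.09-1.11 | 0.885 vs 0.795 |
| 25% / 50% | 16.1 vs 13.9% | 35.4 vs 30.7% | 57.6 vs 51.0% | 1.13-1.16 | 0.885 vs 0.754 |
| 30% / 65% | 15.8 vs 12.2% | 34.7 vs 27.3% | 56.7 vs 46.1% | 1.23-1.29 | 0.865 vs 0.660 |

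**4. Shorter windows.** In the simple model the ST bias is zero by construction. With gradual rescue, 5% vs 15% rescued by Week 26 gives 0.4 to 1.4 points (ratio 1.04), and 5% vs 25% gives 0.8 to 2.8 points (1.08-1.09). Up to Week 32 (32/52.18 = 0.613 years), the simple model with h = 0.3 has 1 − e^(−0.184) = 0.1681 for the unrescued. Placebo is 0.5 × 0.1419 + 0.5 × 0.1681 = 15.5%; drug is 0.25 × 0.1419 + 0.75 × 0.1681 = 16.2%; ratio 1.04.

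**5. The SAP 3.4.1 rate.** Expected events divided by expected time, ∫ h·e^(−ht)·S(t) dt / ∫ e^(−ht)·S(t) dt, equals h whatever S(t) is. Every scenario in step 3 returns 20.0, 50.0 or 100.0 per 100 patient-years in both arms.

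**6. Rescue related to hypoglycaemia risk.** Let half of each arm be rescue-prone, with a quarter of the others' hazard (0.125 vs 0.5). All of these are rescued at Week 26 on placebo and half of them on drug. First-event probabilities are 0.3924 (others, 52 weeks), 0.1171 (prone, 52 weeks) and 0.0604 (prone, 26 weeks).
- Drug: 0.1962 + 0.25 × 0.1171 + 0.25 × 0.0604 = 24.1%.
- Placebo: 0.1962 + 0.5 × 0.0604 = 22.6%.

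The gap falls to 1.4 points (2.6 if the others' hazard is 1.0). It is nil if prone subjects have no hypoglycaemia. Dividing each class's events by its hazard gives 0.747 and 0.634 patient-years, so the rates are 32.2 vs 35.7 per 100 patient-years, ratio 0.90. The rate then errs the other way.

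**7. Regardless of rescue.** If insulin adds no risk, these tables are unbiased. If it doubles the hazard, 25% vs 50% rescue gives 19.8 vs 21.8%, 42.2 vs 45.7% and 66.3 vs 70.0%, drug vs placebo: the opposite direction.

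**The case against.** A reader might infer that the plan will overstate the drugs' hypoglycaemia risk. The documents do not support that as fact. It needs more rescue insulin on placebo and a hazard not much lower in rescue-prone subjects. Such subjects have high FPG or HbA1c and plausibly have fewer low-glucose events.

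A reader might also infer that the plan has no safeguard. It has several: the regardless-of-rescue tables, the up-to-Week-32 tables, the rate defined in 3.4.1, and the pre-rescue rates that Table 24 lists for the overall AE summary. These narrow the gap but leave it open. The first can err in the opposite direction, so the pair may bracket the truth without locating it. The second is still a crude proportion. The overall summary is not split by ADA or ISPAD class.

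Two further points stand. The 52-week placebo column is mixed anyway, because two of every three eligible placebo subjects who enter the third randomisation switch to active drug; neither the model nor the rate removes that. And the tables are descriptive. The 2.9-point example compares with a standard error of √[(0.230 × 0.770 + 0.201 × 0.799)/81] = 6.5 points. The shift is, however, systematic, and it grows with the difference in rescue.

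**Conclusion.** The concern holds in limited form. The classified pre-rescue tables carry no measure of time at risk, although rescue depends on efficacy. At an equal hazard independent of rescue, the ST+LT table shows a drug-to-placebo ratio of about 1.1 to 1.3 under assumed rescue of 20-35% vs 40-65%. ST and up-to-Week-32 effects are small. Equal rescue, or no hypoglycaemia risk in rescue-prone subjects, gives none.

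One might go further and make the rate the new primary measure with a between-arm interval. Step 6 argues against replacing the proportions, since the rate has its own bias when rescue is related to hypoglycaemia risk.

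The documents also disagree on what is primary. SAP 4.7.2.4 makes pre-rescue data primary, while the hypoglycaemia row of Table 24 labels pre-rescue as sensitivity. Protocol 8.4.3.1 names hypoglycemia among the pre-rescue sensitivity analyses and then makes pre-rescue primary. Table 8 places serious hypoglycaemia in the SAE row, whose primary analysis is not cut at rescue, although 4.7.2.4 includes serious events in its pre-rescue tables.

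**What to change.** In SAP 4.7.2.4 and Table 24, add the SAP 3.4.1 exposure-adjusted rate per 100 patient-years to the pre-rescue ST+LT and ST tables, by ADA and ISPAD class. Time at risk should end at the earliest of first event, rescue insulin and end of exposure. Show it beside the proportions and interpret the two together; a between-arm confidence interval is optional.

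In the same edit, reconcile SAP 4.7.2.4, Table 8, Table 24 and protocol 8.4.3.1-8.4.3.2 on which analysis is primary and whether serious events are cut at rescue. Either carry the protocol 8.4.3.2 rates for hypoglycemia into 4.7.2.4 or list the departure in SAP Section 6.

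The cost is SAP wording and a few table columns; no new data are needed. The downside is that the rate still assumes that rescue is unrelated to hypoglycaemia risk, which a table footnote should say.

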4.7.3 Laboratory evaluations

Safety laboratory evaluations performed by central laboratories will be included in summary tables and both central and local laboratory evaluations will be included in the listings. The laboratory data will be presented in Conventional (US) Units and additional presentations for changes from baseline will be repeated using SI units.

Summaries of laboratory data will include assessments up to the cut-off dates defined for each period and parameter in Table 8. Visit windows are provided in Section 4.1.7.1 in order to link each laboratory test to a scheduled visit. All continuous laboratory parameters specified in

Section 3.4.4 will be summarised at each scheduled time point by treatment group using descriptive statistics (including data regardless of rescue medication initiation) during:

- The combined ST+LT period. Observed and change from baseline values will be summarised by treatment group based on the treatment received during the ST period (dapagliflozin/saxagliptin/placebo) using the Treated Subjects Data Set.
- The combined ST+LT period, up to Week 32. Observed and change from baseline values will be summarised by treatment group based on the treatment received during the ST period (dapagliflozin/saxagliptin/placebo) using the Treated Subjects Data Set.
- The randomised withdrawal period. Observed and change from withdrawal baseline values will be summarised for the first two treatment comparisons described in Section 4.1.5 using the Randomised Withdrawal Subject Data Set.

Additionally, eGFR will also be described by age group (using the randomisation strata) for the ST+LT and randomised withdrawal periods using SI units.

Marked abnormality laboratory assessment will be summarised using central laboratories assessments during the ST, the combined ST+LT and randomised withdrawal periods for both conventional and SI units.

Haematology, chemistry and urinalysis laboratory data for the ST+LT period will be listed using both conventional and SI units where applicable. For the ST+LT + Week 104 period, the listing will include all data collected up to Week 104. Flags will be applied to values falling outside reference ranges (which will be explicitly noted on these listings where applicable). Treatment at the time of a laboratory assessment will be included in the listings and will correspond to the last dose received by a subject up to and including the date/time of the laboratory assessment.

Laboratory data values of the form of “< x” (i.e., below the lower limit of quantification) or > x (i.e., above the upper limit of quantification) will be imputed as “x” in the calculation of summary statistics but displayed as “< x” or “> x” in the listings. For determining if the values are out of range or falling within the MA lab criteria, if a value is reported as “<x” or “>x” where x is the lower or upper criteria respectively, then this will be reported as “low” or “high” respectively for the reference range indicator and as meeting the MA criteria.

Note that prior to database lock and unblinding, analysis data for urinary glucose, and urinary glucose: creatinine ratio will be based on dummy values (to preserve the blind).

